2. INTRODUCTION

Aclaris Therapeutics, Inc. is developing ATI-50002 Topical Solution for the treatment of non-segmental vitiligo of the face. ATI-50002 is a potent highly selective inhibitor of Janus kinase 1 (JAK1) and Janus kinase 3 (JAK3).

2.1. Summary

Overview of Vitiligo

Vitiligo is an autoimmune dermatologic condition characterized by patchy depigmentation of the skin due to loss of cutaneous melanocytes. The affected skin lacks epidermal melanocytes, whereas hair follicles within the lesional skin are often spared, likely due to the immune privilege of the hair follicle. Vitiligo affects 1-2% of the world's population, occurring in all races and both genders (Fitzpatrick T, Mosher D, 2017) (NIAMS 2017). People with vitiligo may be at increased risk of social or psychological distress, sunburn, eye problems, such as inflammation of the iris (iritis), and hearing loss. There is a genetic predisposition to vitiligo. The average age of vitiligo onset is about 20 years, with onset most commonly observed between the ages of 10 and 30 (Fitzpatrick T, Mosher D, 2017).

There are several clinical classifications of vitiligo. Segmental vitiligo presents as one or more macules in a unilateral distribution. All other types of vitiligo are classified as non-segmental vitiligo (NSV), which is most common.

NSV occurs most often on the face, followed by the trunk. Depigmented patches typically evolve over time, vary in size from a few to several centimeters in diameter, are flat areas of normal-feeling skin, and may have a hyperpigmented edge (Ezzedine K, et al. 2012). The edges typically are well-defined but irregular. Body hair typically remains pigmented although hair depigmentation may occur with disease progression. Scalp involvement and other hair bearing areas may appear with patches of white or gray hairs.

Focal vitiligo is characterized by depigmentation in one area, or macule. Other forms of non-segmental vitiligo often produce symmetric patches, sometimes covering large areas. Mucosal vitiligo affects only mucosal membranes. Generalized vitiligo may be acrofacial, in which depigmentation occurs on the distal fingers and periorificial areas, or vulgaris, which is characterized by widely distributed, scattered patches. Universal vitiligo manifests as complete or nearly complete depigmentation, and frequently is associated with multiple endocrinopathy syndrome.

Recent observations have pointed to a role for cellular immunity in the pathogenesis of vitiligo (Wang et al. 2011). Pathogenesis incorporates both intrinsic defects within melanocytes that activates the cellular stress response as well as autoimmune mechanisms that target these cells (Rashighi M, Harris JE, 2017). Despite some advances in explaining the origins of the disorder, current therapies, such as topical corticosteroids, topical immunomodulators and psoralen phototherapy may have serious side effects and limited therapeutic utility. Vitiligo is a disfiguring disease for which current therapies have proven unsatisfactory.

Immunopathology and Pathophysiology of Vitiligo

Over the past two decades, basic and translational research studies have identified several pathogenic pathways that promote vitiligo (Rashighi M, Harris JE, 2017) (Frisoli ML, Harris JE, 2017). These immune pathways prominently involve interferon- γ (IFN- γ) dependent chemokines and CD8 $^{+}$ T-cells. Signaling by Janus kinases (JAKs) is pivotal to these pathogenic pathways (Villarino et al, 2015). As such, inhibition of IFN- γ using JAK inhibitors is a leading candidate for a clinical treatment strategy. Of the JAK sub-types, JAK1 and JAK3 are associated with vitiliginous pathology.

ATI-50002 is a JAK1/3 inhibitor with enzyme IC₅₀ activities of 2nM and 36nM against JAK1 and JAK3, respectively (Data on file). At a cellular/physiologic level, ATI-50002 inhibits interferon- γ -induced pSTAT1 activation with an IC₅₀ of 38nM (Data on file). The anticipated IC₉₀ concentration is approximately 0.4 μ M. To expect ATI-50002 to inhibit JAK1/3-mediated signaling, a significant excess of the inhibitor must be present in the target tissue. Based upon tissue penetration studies (Franz chamber with human skin) using the 0.46% ATI-50002 formulation, extrapolated ATI-50002 concentrations were found to be in the range of 10-20 μ M (Data on file). A 10 μ M concentration should deliver drug to epidermis and dermis at levels anticipated to achieve inhibition of JAK1/3 signaling and inhibit T-cell-mediated melanocyte depletion.

Vitiligo Treatments

Existing treatments include topical and systemic immunosuppressants, phototherapy, and surgical techniques, which together may serve to arrest disease progressions, stabilize depigmented lesions and encourage repigmentation. Depigmentation creams are used in cases where repigmentation therapies are ineffective or greater than 50% BSA is involved. Current treatments for vitiligo are only moderately effective and are both financially and practically burdensome (Frisoli ML, Harris JE, 2017). Topical immunosuppressants, which suppress immune responses in the superficial skin where the immune infiltrate is located are most useful in treating disease that is localized, comprising less than 5% of the body surface area (BSA) (Frisoli ML, Harris JE, 2017). Phototherapy is effective for more widespread disease, or disease that is active and expanding with the appearance of new lesions. Excimer laser is also effective when treating localized disease that is unresponsive to topical therapies, or when a more rapid response is desired. Highly active, vitiligo can be stabilized through oral pulse steroid therapy, which is continued until another therapy (is therapeutic (Frisoli ML, Harris JE, 2017).

Vitiligo responds slowly to treatment, with early signs of repigmentation visible within 2-3 months of initiating treatment, and significant improvement taking up to 6 months to observe (Frisoli ML, Harris JE, 2017). Biomarkers may serve as excellent early indicators of treatment responses. These include both serum biomarkers as well as biomarkers that can be directly measured within lesional skin.

3. STUDY RATIONALE

3.1. Study Rationale

Preclinical and preliminary clinical information suggests that blockade of the IFN- γ pathway may treat vitiligo. Inhibitors of the JAK/STAT pathway, particularly JAK1 and JAK3, are known to downregulate the effects of IFN- γ (through the inhibition at JAK1). Two case reports have demonstrated the potential for compounds that are JAK inhibitors (ruxolitinib and tofacitinib) to repigment areas of vitiligo in patients (Craiglow BG, King BA, 2015) (Harris JE, Rashighi M, Nguyen N, et al, 2016). In a recent study in a small cohort of patients, treatment with topical ruxolitinib for 20 weeks produced significant improvement in facial vitiligo (Rothstein BA et al., 2017). As ATI-50002 is a potent inhibitor at JAK1 and JAK3, it is strongly suggested that ATI-50002 may be effective in the treatment of vitiligo.

This study will evaluate the safety, tolerability and efficacy of ATI-50002 Topical Solution, 0.46% applied twice-daily for up to 48 weeks in subjects with non-segmental facial vitiligo.

4. STUDY OBJECTIVES

4.1. Primary Objective

The primary objective of this study is to assess the safety, tolerability and efficacy of ATI-50002 Topical Solution, 0.46% in subjects with non-segmental facial vitiligo.

4.2. Secondary Objectives

Secondary objectives include:

- Assessment of the subject's satisfaction with repigmentation following treatment using the Subject Vitiligo Satisfaction scale (SVSS).
- Assessment of the impact of vitiligo of the subject's quality of life using the Vitiligo-Specific Quality-of-Life Instrument (VitiQoL).

5. SELECTION AND DISPOSITION OF STUDY POPULATION

5.1. Number of Subjects and Study Sites

A total of 33 subjects will be enrolled at approximately 5 US sites.

5.2. Study Population Characteristics

Male and female subjects, \geq 18 years old, with a clinical diagnosis of new onset or actively progressing non-segmental facial vitiligo or worsening of existing facial vitiligo within the past 6 months.

5.3. Inclusion Criteria

In order to be eligible for the study, a subject must fulfill all of the following criteria:

1. Subject is a male or female \geq 18 years of age.
2. Subject has a clinical diagnosis of new onset or actively progressing non-segmental facial vitiligo or worsening of existing facial lesions within the past 6 months. Actively progressing vitiligo is defined as: subject history of a new vitiliginous lesion or objective signs of disease activity (such as: confetti-like depigmentation, trichrome lesions, and the Koebner phenomenon) as assessed by the investigator. Subjects may have non-facial vitiliginous lesions that are unchanged for more than 6 months provided they meet the requirement for active facial lesions.
3. Subject has non-segmental facial vitiligo effecting at least 0.25% total body surface area (TBSA) (excluding: the area from the eyebrows to and including the upper eyelids, the area from the bony rim of the orbit to and including the lower eyelids; mucosal lip areas; beard [if applicable]; and forehead and chin areas covered by the stereotactic positioning device for photography) with at least one area of the face with normal pigmentation. The face is defined as the area from the border of the hairline, not including hair bearing skin (eyebrows and beard, if applicable) to the jawline.
4. Women of childbearing potential (WOCBP) must have a negative serum pregnancy test at the screening visit and a negative urine pregnancy test at the baseline visit and must agree to use an approved method of highly effective birth control for the duration of the study and for 30 days after last study medication application.
5. If female, subject who is non-pregnant and non-lactating and not planning a pregnancy during the duration of the study.
6. Subject is in good general health and free of any known disease state or physical condition which, in the opinion of the investigator, would interfere with the study assessments or put the subject at undue risk by study participation.
7. Subject is willing and able to follow all study instructions and to attend all study visits.
8. Subject agrees to refrain from any other treatments for vitiligo from the screening visit through the final follow-up visit. Over the counter (OTC) preparations deemed acceptable by the investigator and camouflage makeups are permitted.
9. Subject is able to comprehend and willing to sign an Informed Consent Form (ICF).
10. Sexually active male subjects with a partner who is a WOCBP, must agree to use a barrier method of contraception from the first application of study medication to at least 30 days after the last dose of study medication.

5.4. Exclusion Criteria

Any subject who meets one or more of the following criteria will not be included in this study:

1. Subject with evidence of poliosis (white hairs) in $> 50\%$ of their facial vitiligo lesions.
2. Subject with total facial depigmentation.
3. Subject with significant spontaneous ongoing repigmentation (documented based on the subject's reporting in the last 3 months).
4. Subject who has segmental vitiligo.
5. Subject who has failed phototherapy. Failed phototherapy is defined as failure to achieve satisfactory repigmentation following adequately delivered phototherapy as determined by the investigator.

6. Subject currently has, or has a history of, skin disease (e.g., psoriasis, seborrheic dermatitis, etc.) that, in the opinion of the investigator, would interfere with the study medication application or study assessments.
7. Subject has, or has a history of, severe, progressive or uncontrolled autoimmune, metabolic, renal, hepatic, gastrointestinal, pulmonary, cardiovascular, genitourinary (i.e., renal disease), hematological disease, neurologic or cerebral disorders, infectious disease or coagulation disorders that, in the opinion of the investigator, would interfere with the study assessments or put the subject at undue risk by study participation.
8. Subject currently has a history of, current, or suspected systemic or cutaneous malignancy and /or lymphoproliferative disease, other than a history of adequately treated, well healed and completely cleared non-melanoma skin cancers (e.g., basal or squamous cell carcinoma) treated successfully at least 1 year prior to study entry with no evidence of disease.
9. Subject currently has evidence of active or latent bacterial (including tuberculosis) or viral infections at the time of enrollment, or a history of incompletely treated or untreated tuberculosis. Subjects who have initiated therapy for latent tuberculosis for at least 2 weeks and agree to continue their therapy through completion may participate.
10. Subject has a history of serious local infection (e.g., cellulitis, abscess) or systemic infection, or history of treated infection (e.g., pneumonia, septicemia) within 3 months prior to the baseline visit. Subjects on an antibiotic for a nonserious, acute local infection must complete the course prior to enrollment into the study.
11. Subject has herpes zoster or cytomegalovirus (CMV) that resolved within 8 weeks prior to Visit 1.
12. Subject has a history of frequent outbreaks of oral Herpes Simplex Virus defined as more than 4 episodes per year.
13. Subjects previously treated with depigmenting agents.
14. Clinically significant laboratory abnormalities at screening that in the opinion of the investigator, would make the subject a poor candidate for the study. Subjects with any other Screening laboratory values meeting the Study Medication Interruption Criteria found in Table 1 must have repeat lab testing performed with results meeting the minimum criteria for resumption in order to initiate treatment at Baseline (Visit 2).
15. Subject who has an absolute neutrophil count <1,800/ μ L, or platelet count < 130,000/ μ L.
16. Subject unable to comply with the required washout periods:
 1. Use of any biologic, investigational therapy or procedure for vitiligo within 12 weeks or 5 half-lives (whichever is longer) of screening (Visit 1).
 2. Use of laser or light-based vitiligo treatments, including tanning beds, within 8 weeks of screening (Visit 1).
 3. Use of immunomodulating oral or systemic medications (e.g., corticosteroids, methotrexate, cyclosporine) or topical treatments that may affect vitiligo (e.g., corticosteroids, tacrolimus/ pimecrolimus, retinoids) within 4 weeks of screening (Visit 1).
 4. Use of any prior concomitant therapy not listed above that may interfere with the objective of the study as per the discretion of the investigator, including drugs that cause photosensitivity or skin pigmentation (e.g., antibiotics such as tetracyclines, sulfa, tranexamic acid, etc.) within 8 weeks of screening (Visit 1).

5. Subjects who have previously received oral or topical JAK inhibitors.
17. Subject who has participated in any investigational drug or device trial, regardless of indication in which administration of an investigational drug or device occurred within 30 days or 5 half-lives (whichever is longer) of screening (Visit 1). Note that investigational treatment for vitiligo (in any body area) requires a longer washout – see Exclusion criterion #16.1 above.
18. Subjects with a clinically significant abnormal thyroid-stimulating hormone or free T4 at screening. Subjects under treatment with stable thyroid replacement who have a free T4 and TSH within the normal range may participate.
19. Subject has history of sensitivity to any of the ingredients in the study medications.
20. Subject has a history of, or current alcohol or drug abuse within 2 years of study enrollment
21. Screening ECG findings of:
 1. QTcF >450msec for males or >470msec for females (use of the ECG algorithm is acceptable for this purpose)
 2. Clinically significant heart rate ≤ 45 or Heart Rate ≥ 100 beats/minutes
 3. Rhythm disturbance other than sinus arrhythmia or ectopic supraventricular rhythm (ectopic atrial rhythm)
 4. Conduction disturbance including PR >240msec, pre-excitation (delta wave and PR <120msec), second degree or higher AV block
 5. Acute or chronic signs of ischemia.
 6. Left Bundle Branch Block
 7. Prior myocardial infarction
22. Positive for HIV, Hepatitis B or C. Subject with serologic evidence of Hepatitis B vaccination (HepB surface Ab without the presence of Hep B sAg) will be allowed to participate.

5.5. Previous and Concomitant Medications and Therapies

At Screening (Visit 1), the Investigator or designee will question the subject to ensure they have not used any excluded therapies (Section 5.6.1). Concomitant therapies are any new or existing therapies received from Screening (Visit 1) until Week 52 (Visit 15). Concomitant therapies include drug (e.g., prescription and over the counter [OTC]), and non-drug (e.g., chiropractic, physical therapy, energy-based) treatments.

5.6. Permitted Concomitant Medications, Therapies and Over the Counter Products (OTC)

All topical products used on the face and neck should be reviewed by the investigator or designee and are permitted, if in the opinion of the investigator or designee will not affect the safety or efficacy of the subject during the study. Subjects will be allowed to take medications not restricted by the protocol as long as they have been on a stable dose prior to study entry. Vitamins, minerals, and dietary supplements are permitted during the study, if the subject has been on a stable dose prior to study entry and, in the opinion of the Investigator, will not affect the safety or efficacy of the subject during the study.

Topical therapies such as topical corticosteroids are permitted as long as they are not applied on or near the face and treated areas of the neck. Inhaled or intranasal corticosteroids are allowed in

the study. Male subjects who shave at screening and baseline should maintain the same shaving regimen during the study.

NB-UVB treatments may be administered according to the Standard of Care protocol for the treatment of vitiligo after the subject has completed Visit 9. NB-UVB treatments should be recorded in the source documents and on the Concomitant Therapies Log of the eCRF.

Prior permitted concomitant medications taken within 30 days of beginning treatment with ATI-50002 Topical Solution will be documented in the subject's source document and eCRF. In addition, any new permitted medications administered during protocol treatment and through Week 28 (Visit 11) will be documented in the subject's source document and eCRF.

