8.1. Assessments of Efficacy

8.1.1. Canfield 2D Digital Facial Image Analysis

A qualified investigational staff member will take 18 photographs (5 lighting modalities x 3 views [left, front, right]) of the face at baseline and then monthly during the study. Each imaging session includes a sequence of images including the following lighting/capture modalities:

- Standard 1 (default settings) – General purpose white light photograph, the typical “clinical” photo. Provides balanced cross lighting for good subjective evaluation of most skin features.
- Standard 2 (default settings) – ‘Diffuse light’. Provides even, white light across the entire image with a minimum of highlight and shadow. Ideal for many quantitative image analysis applications.
- Cross Polarized (default settings) – Polarized light sources with a Perpendicular polarizer over the camera lens. Filters out surface reflections for superior visualization of sub-surface detail (vascular features, erythema, pigment, etc.)

- UV Fluorescence - NF (default settings) – UV filters (365nm band pass) over powerful strobes captured through an un-attenuated lens. The Fluorescence photo is geared toward enhancing the visibility of pigment features that absorb UV light. Fluorescing Porphyrin details are also visible.
- Parallel Polarized (default settings) – Polarized light sources with a Parallel polarizer over the camera lens. Passes only surface reflections for superior visualization of topographical data (wrinkles, fine lines, pores, etc.)

Equipment, supplies, training and detailed instructions for obtaining and managing photographs will be provided to the investigational center prior to the initiation of subject enrollment.

Canfield Scientific will conduct image analysis. The obtained cross-polarized image will be transformed using Canfield's RBX technique to separate melanin (Brown image) from hemoglobin (Red image). A segmentation algorithm detects hyperpigmentation (pigmented areas with concentration higher than normal skin concentration) and depigmentation (pigmented areas with concentration lower than normal skin concentration) within the areas of interest (AOI) from the RBX Brown images. Area of detected pigmentation and intensity measurements can be reported by the algorithm after segmentation. The measurement will be the ratio of the detected area of pigmentation and the AOI. The primary endpoint will be based on the quantification of depigmentation in the AOI over time.

Area of Interest

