The AOI includes approximately 90% of the total facial surface area and is defined as the area from the border of the hairline to the jawline. Hair bearing areas such as the eyebrows and the areas of the forehead and chin covered by the stereotactic positioning device for photographs are not included in the AOI. Refer to APPENDIX 6 for a diagram of the AOI.

8.1.2. Facial Vitiligo Area Scoring Index (F-VASI) and Facial Total Body Surface Area (TBSA)

The F-VASI is an assessment of the subject's facial vitiligo modified from the VASI for the face only. The investigator or designee will assess the face using a Wood's lamp to assist in the identification of the vitiliginous lesions and then calculate the F-VASI score based on the descriptor that best matches the presentation of the subject at each individual visit: Baseline (Visit 2) and Visits 5, 6, 7, 8, 9, 10,11 (if applicable) and if continuing for 24 additional weeks of treatment, Visit 12-15. The investigator should not refer to any other visits assessments when performing the F-VASI.

The percentage of vitiligo involvement for the face is calculated using the palmar method. The palmar method uses the palmar surface area of the investigator's hand as an estimation guide and defines the surface of the hand including fingers to be 1.0% of the total body surface area.

At screening and baseline, the **Facial TBSA** will be calculated and must be at least 0.25% (excluding: the area from the eyebrows to and including the upper eyelids; the area from the bony rim of the orbit to and including the lower eyelids; mucosal lip areas, and the area of the chin and forehead covered by stereotactic photographic device) and include at least one area of normal pigmentation. The face is then clinically evaluated by visual assessment for the pattern

of skin depigmentation using a visual scale. The publication by Hamzavi I, Jain H, McLean D, Shapiro J, Zeng H, and Lui H. 2004 will be provided to the investigators to depict the pattern of depigmentation as illustrated in descriptive patient photographs.

Facial VASI = % BSA x residual depigmentation

- **BSA** - used as a guide to estimate % of vitiligo involvement of the face
- **Extent of residual depigmentation** is expressed by the following percentages:
 - 0
 - 10% - only specks of depigmentation are present
 - 25% - the pigmented area exceeds the depigmented area
 - 50% - the depigmented and pigmented areas are equal

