APPENDIX 6: Area of Interest

The area of Interest (AOI) mask template will be applied to all images obtained in the study. The following guidelines will be used to delineate boundaries for the AOI. For the Left and Right Oblique image template, horizontal and vertical guidelines will be placed at the outer canthus as well as a vertical guideline at the commissure and the center of the lip. For boundary points not defined by these guidelines, Canfield may adjust the template points along the brow line, hairline, jawline, lip line, beard, nose tip and/or bridge, and top of the cheek bone.

For the Frontal template, vertical guidelines will be placed at the outer canthi and a horizontal guideline will be placed at the right inner canthus to delineate the edges of the AOI. For the boundaries not defined by these guidelines, Canfield may adjust the template points along the brow line and headrest (see Figure 1).

Figure 1: Area of Interest Diagram

The Facial VASI should be calculated based on the depigmented areas within the mask template above excluding the facial areas covered by a beard, if applicable. Study staff may instruct the subject to treat the areas of depigmentation which are blocked by the stereotactic device (forehead and chin) and the eyebrow area down to the level of the bony rim of the orbit and the beard, if applicable.

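### The shaving rule leaves out men who are bearded at baseline, so a beard change can alter the skin counted in F-VASI and in the primary image ratio without any repigmentation

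*Combined protocol and SAP*

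**What the plan says.** Section 5.6 states: "Male subjects who shave at screening and baseline should maintain the same shaving regimen during the study". Nothing else in the protocol governs facial hair during the study. The consistency rules in Sections 6.2 and 8 concern the assessor, lighting and positioning. The subject instructions in Appendix 1 do not mention shaving.

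Bearded men may enrol. Inclusion criterion 3 (Section 5.3) only leaves the beard out of the 0.25% entry area.

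For the primary measure, Section 8.1.1 says: "The measurement will be the ratio of the detected area of pigmentation and the AOI". It places outside the AOI "Hair bearing areas such as the eyebrows and the areas of the forehead and chin covered by the stereotactic positioning device". Appendix 6 says: "The area of Interest (AOI) mask template will be applied to all images obtained in the study". For the oblique views it adds that "Canfield may adjust the template points along the brow line, hairline, jawline, lip line, beard, nose tip and/or bridge". For the frontal view the permission is narrower: "Canfield may adjust the template points along the brow line and headrest". The plan does not say whether a subject's mask is locked at baseline or re-fitted at each visit.

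For F-VASI, Appendix 6 bases the score on depigmented areas inside the mask, "excluding the facial areas covered by a beard, if applicable". Section 8.1.2 defines the score as percentage body surface area multiplied by residual depigmentation, and tells the investigator not to consult other visits when scoring.

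**The concern.** A change from baseline is interpretable only if both visits measure the same skin. Here the counted skin can depend on the beard worn on the day, and the one rule that would hold it constant is addressed to men who already shave. A beard removed or extended between Visit 2 and Visit 14 can therefore change the measured area while pigmentation stays the same.

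The protocol also lets subjects treat skin under the beard (Synopsis and Appendix 6). A man who later shaves may thus bring treated skin with no baseline value into the comparison.

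The trial has a single arm, and its primary result is a mean change in about 33 subjects (Sections 11.1 and 11.2). No concurrent group would show the same artefact and cancel it. The plan does not ask for beard status to be recorded and has no analysis rule for a change.

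**Working it through.** The plan gives no figure to reproduce: no power calculation, SD, number of bearded men or beard share. The check reads the two definitions and applies plain arithmetic. Every depigmentation fraction and beard share below is an assumption, and true repigmentation is zero throughout.

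**F-VASI.** Score = % BSA × residual depigmentation. Hold the residual grade at 100%, with 0.50% BSA of vitiligo visible and 0.10% to 0.25% under the beard.
- Shaving: 0.50 → 0.60 (+20%) up to 0.50 → 0.75 (+50%).
- Beard growing over the same skin: 0.60 → 0.50 (−17%) up to 0.75 → 0.50 (−33%).
- With no vitiligo under the beard, the score does not move.

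At a given residual grade, shaving can only raise or leave the score. Growth can only lower or leave it, which would look like improvement.

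**Image ratio, shaving, oblique mask re-fitted to take in the shaved skin.** Let p be the depigmented fraction outside the beard, q the fraction under it, and b the beard's share of the new AOI. New ratio = (1 − b)p + bq. With p = 20% and b = 20%:

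| q | New ratio | Shift |
|---|---|---|
| 0% | 0.8 × 20% + 0.2 × 0% = 16% | −4 points |
| 20% | 16% + 4% = 20% | 0 |
| 40% | 16% + 8% = 24% | +4 points |

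For b from 10% to 30%, the shift is −2 to −6 points at q = 0% and +2 to +6 points at q = 40%.

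**Image ratio, shaving, fixed mask.** If the mask excludes the beard, nothing changes. If it includes the beard and the hair had hidden white skin, the ratio rises or stays the same.

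**Image ratio, beard extending** over a share g of the AOI in which half the skin is white, starting from 20%:
- Fixed mask, if hair reads as pigment: 20% − 0.5g = 17.5% at g = 5% and 15% at g = 10%.
- Re-fitted mask: (20% − 0.5g)/(1 − g) = 17.5/0.95 = 18.4% and 15/0.90 = 16.7%.

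**Effect on the mean.** Suppose k of 33 subjects each shift by 4 points in the same direction. The mean moves by 4k/33: 4/33 = 0.12 points for k = 1 and 20/33 = 0.61 points for k = 5. Opposite shifts would partly cancel. If fewer than 33 subjects have Week 48 images, each affected subject weighs proportionately more.

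**The case against.** The strongest reply is that the image effect depends on premises the plan does not state. A reader might infer that shaving gives a false improvement from 20% to 16%, a fall of one fifth. That requires the mask to be re-fitted, which Appendix 6 allows along the beard only in the oblique views. It cannot happen under a fixed mask. How hair registers in the melanin image is also inferred: Section 8.1.1 does not mention it, and hair in lesions may itself be white, since exclusion criterion 1 bars poliosis only above 50% of facial lesions. These points stand, so the image effect is conditional.

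A reader might also infer that any man with a beard is free to let it spread. A man who shaves around a partial beard does shave at screening and baseline, and is arguably bound already. The gap for spread therefore concerns mainly men who do not shave.

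Finally, the analysis is descriptive, the study is a pilot, and part of the chin is already outside the AOI, which limits the beard's possible share. This is fair as to size. It does not answer the F-VASI route, which needs no assumption about re-fitting: beard-covered skin is excluded and each visit is scored without reference to the others.

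**Conclusion.** The concern holds in a limited form. A man who is bearded at baseline may shave, and a non-shaver may let the beard extend, without breaching the protocol. This can change the skin counted in F-VASI, in a known direction for each kind of change. It can change the primary image ratio in either direction under a re-fitted oblique mask, or through hair covering AOI skin under a fixed one.

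The documents do not support saying that a beard change always alters either measure. The re-fitted ratio stays put when skin under the beard is as depigmented as the rest, and F-VASI stays put when there is no vitiligo under the beard. Nor do they support calling the primary result materially biased. The illustrative effect on the mean, 0.12 to 0.61 points, rests on an assumed 4-point shift in 1 to 5 of 33 subjects. For the individual man the distortion could be considerable. The gap merits correction mainly because closing it costs so little.

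**What to change.** Replace the Section 5.6 sentence with: 'Subjects should keep the facial-hair state shown in the baseline photographs (clean-shaven, or bearded with the same outline) until their last photography visit.' Put the same line in the subject instructions in Appendix 1.

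Flag any change at each photography visit. Where a change occurred:
- **Image ratio:** recompute from the stored images, using only skin that was beard-free at both baseline and that visit.
- **F-VASI:** report a sensitivity analysis that omits the flagged visits. Past live examinations should not be re-scored: a Wood's-lamp reading cannot be restricted to common skin afterwards, and Section 8.1.2 bars reference to other visits.

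The cost is one protocol sentence, one instruction line, one eCRF item and recomputation of a few images. The small downside is that bearded men are asked not to change their beard during the study.
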